9.3.1 Exposures

Afatinib:

Patients will be treated with afatinib 30 mg or 40 mg tablet once daily as indicated in the approved labels of afatinib.

3rd generation EGFR TKI or other subsequent treatment:

Patients may be treated with 3rd generation EGFR TKI or other subsequent treatment as indicated in the approved labels.

The Summaries of Product Characteristics on Giotrif® is contained in the ISF in the “Summary of Product Characteristics” (SmPC) section.

9.3.2 Outcomes

9.3.2.1 Primary outcomes

Time on treatment of afatinib as first-line therapy in advanced non-small cell lung cancer patients with EGFR mutation. Time on Treatment (TOT) is defined from the start of afatinib treatment until the end of the afatinib treatment. Patients that are lost to follow up or withdraw before the end of study will be censored at the time of last known contact.

9.3.2.2 Secondary outcomes

- Overall Survival(OS) from the start of afatinib until the end of study, date of death, patient withdrawal or loss to follow-up
- ORR [OR is defined as best overall response of CR and PR] according to RECIST 1.1 by investigator review with afatinib in first-line treatment
- AEs, SAEs, afatinib-related AEs (ADRs) as indicated by incidence seriousness and intensity graded according to United States (US) national cancer institute's (NCI) (CTCAE Version 5.0)

9.3.3 Covariates

As mentioned previously, the data from study 1200-0066 will be used to assess presence of potential channelling bias and to put the results into perspective. Therefore, the baseline characteristics of patients in 1200-0066 trial will be described. The covariates to be collected in the both studies (if applicable) are listed as following.

- Baseline demographic: age, gender, height, weight, body mass index, , smoking status (former, current, never)
- Clinical characteristics including medical history, surgery history, lab testing information (haematology, biochemistry and urine examinations), disease stage, tumour histological classification, EGFR mutation at start of afatinib therapy, ECOG PS score, brain metastases, afatinib starting dose
- Current/Concomitant medications

9.4 DATA SOURCES

Data for this study will be obtained via the following sources:

- Patient medical information: The investigator or authorised medical staff will record clinical and treatment data from patients' medical records/laboratory tests/physical examination into an eCRF at baseline and at every visit up to the end of the follow-up period.

There are no protocol-mandated tests, procedures, or clinic visits for this study. All the data will be continuously and directly into the eCRF during or after the patient visit in the whole study period.

9.5 STUDY SIZE

Seventy-six patients will be included in this study.

Based on LUX-Lung trials, we assume the median time on treatment (TOT) on afatinib to be 12 months in this study. Assuming that the time on treatment (TOT) follows an exponential distribution, it is expected to have 35 events till 2 years after last patient in, given total sample size equal to 76, considering a 30% drop out rate.

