Name of finished medicinal product: Giotrif®				
Name of active ingredient: Afatinib				

withdraw before the end of study will be censored at the time of last known contact.
 
Secondary outcomes
 
Overall survival (OS) from the start of afatinib until the date of death, loss to follow up (including patient withdrawal) or end of study period
 
Objective response rate (ORR), [objective response is defined as best overall response of complete response (CR), partial response (PR)] according to RECIST 1.1 with afatinib first-line therapy
 
Adverse events (AEs), serious adverse events (SAEs), afatinib-related AEs (ADRs) as indicated by incidence, seriousness and intensity graded according to United States (US) national cancer institute's (NCI) common terminology criteria for AEs version 5.0 (CTCAE Version 5.0)
 
Further outcome
 
Resistance mechanisms (Type and proportion:T790M,etc) after afatinib first-line treatment.
				
Data sources:	
Data for this study will be obtained via the following sources:
 
- Patient medical information: The investigator or authorized medical staff will record clinical and treatment data from patients' medical records into an electronic case report form (eCRF) at baseline and at every visit up to end of the follow up period (refer to Section 9.4)			
Study size:	76 patients			
Study duration:	The duration of data collection for an individual patient will be a maximum of approximately 33 months, It is anticipated that all data collection for this study started from May 2020(first patient enrolled) and will continue until December 2023 (two years after the last patient was enrolled)			
Data analysis:	
Time on treatment (TOT) will be analysed using Kaplan-Meier method, and the median Time on Treatment (TOT) along with two-sided 90% confidence interval (CI) will be calculated. Overall survival (OS) will be analysed similarly.
 
Objective response rate (ORR) and acquired resistance mutation type, and AEs will be summarised descriptively by frequency and proportions.
			
Milestones:				
IRB/IEC Approval: May 2020				
First Patient In: May 2020				

Name of company: Boehringer Ingelheim		
Name of finished medicinal product: Giotrif®		
Name of active ingredient: Afatinib Last Patient In: Dec 2021 Interim Analysis: Dec 2022 Last Patient Out: Dec 2023 Database Locked: Mar 2024 Final NIS Report: Jun 2024		

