9.2.2 Study duration

It is anticipated that all data collection for this study started from May 2020 (first patient enrolled) and will continue until Dec 2023 or the event of OS . The maximum duration of data collection for an individual patient will be a maximum of 33 months. this period may be truncated due to treatment switching, patient withdrawal from the study, or death or end of study for any other reason.

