9.9.3 Study Sample Size

76 patients were enrolled in this study, this is a small sample size which may impact the assessment of study outcomes. A sample size of 76 patients is expected to ensure an 80% chance to observe the width of the 90% CI of median TOT of afatinib smaller than or equal to 11 months.

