12. PLANS FOR DISSEMINATING AND COMMUNICATING STUDY RESULTS

The rights of the investigator and the sponsor with regard to the publication of the results of this study are described in the investigator contract.

The publication for study design is planned for Dec 2019, the interim analysis for the primary outcome and some secondary outcomes is planned for Dec 2022, and the publication kick-off for primary outcome is planned for Jun 2023 after the interim analysis report is completed. The final publication will be written after the final NIS report is completed in Dec 2024.

BI intends to use data from this study to prepare peer-reviewed publications and other scientific communications such as abstracts, posters, and podiums presentations.

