7.6 PRIMARY ANALYSES

All patients treated with afatinib will be included in the analysis of the primary outcome, Time on Treatment (TOT) on afatinib.

The TOT with afatinib is defined as time from the start of afatinib to last dose date of afatinib or death date by any cause, which comes first.

Refer to Table 7.6: 1 for the rules for determining TOT with afatinib event or censoring date. The analysis of TOT with afatinib will be performed on Treated Set (TS). Those analyses will be conducted as one of the interim analyses mentioned in [section 7.11](#).

Table 7.6: 1 Rules for determining TOT event or censoring date

Rule #	Situation	Outcome	Date of event or censoring
1	Patients lost to follow up without providing end date of treatment during afatinib treatment period	censor	Date of last known date of contact during afatinib treatment period
2	Patients still receive ongoing first-line afatinib treatment at end of study period	censor	Date of last known date of contact during first line afatinib treatment period

Proprietary confidential information © 2024 Boehringer Ingelheim International GmbH or one or more of its affiliated companies

Rule #	Situation	Outcome	Date of event of censoring
3	Other situations	event	Date of last treatment during first line afatinib treatment period

The last known date of contact will derive as follows:

For subjects who withdrew from study or became lost to follow-up, the date last known of contact will be based on the last assessment date/visit date or the date of the last dose of study drug or end of study date, whichever occurs later.

If last known of contact date is later than cut-off date, use cut-off date as last known of contact date.

Kaplan-Meier estimates and two-sided 90% confidence intervals for the 25th, median, and 75th percentiles of the survival distribution will be calculated, the Brookmeyer-Crowley method^[4] based on log-log transformation will be used to construct the 90% CI, the standard error of the Kaplan-Meier quartile estimates will be estimated using Greenwood's formula. Kaplan-Meier curves will also be produced.

For the purpose of calculating TOT, incomplete first line afatinib treatment end dates will be imputed as below:

If month and year are present and day is missing:

- If year=year of first dosing and
 - If month = month of first dose then set day to day of first dose
 - If month > month of first dose then set day to first day of month

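### The 35 expected time-on-treatment events in Protocol 9.5 do not follow from its stated inputs, which give at least about 40, and the precision statement in 9.9.3 needs the same inputs

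*Protocol*

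**What the plan says.** Protocol 9.5 takes a median TOT of 12 months and an exponential distribution, then says "it is expected to have 35 events till 2 years after last patient in, given total sample size equal to 76". The allowance for attrition appears only as "considering a 30% drop out rate". The section does not say whether the 30% is a total, an annual rate or something else, and it gives no accrual pattern.

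Protocol 9.9.3 adds the precision claim, namely that this sample should "ensure an 80% chance to observe the width of the 90% CI of median TOT of afatinib smaller than or equal to 11 months". It gives no separate inputs for that probability.

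The calendar is in the abstract and in section 6: first patient in May 2020, then "Last Patient In: Dec 2021", with last patient out in December 2023. Section 9.2.2 adds a cap on follow-up: "The maximum duration of data collection for an individual patient will be a maximum of 33 months".

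The interval method is in SAP 7.6: "two-sided 90% confidence intervals for the 25th, median, and 75th percentiles of the survival distribution will be calculated, the Brookmeyer-Crowley method", on the log-log scale.

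**The concern.** The follow-up in 9.5 is long relative to the assumed median. Everyone who stays in the study is observed for at least 24 months, which is two medians, so three quarters or more of them should stop treatment within that time. Against 76 patients and 30% dropout, 35 events looks too few.

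These two sentences are the only quantitative support for N = 76 and for the precision of the primary outcome. If they rest on different dropout assumptions, or on one heavier than the 30% stated, a reader cannot tell how much attrition the design was meant to tolerate. That matters here because loss to follow-up is a limitation the protocol itself names in 9.9.1.

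**Working it through.** **Inputs from the documents.** N = 76, exponential TOT, median 12 months, 30% dropout and a cut 24 months after last patient in (Protocol 9.5); accrual May 2020 to December 2021, about 19 months (Protocol 6); 33-month cap (Protocol 9.2.2); two-sided 90% Brookmeyer-Crowley log-log interval (SAP 7.6).

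**Assumed, not in the documents.** Uniform entry over the 19 months; dropout independent of TOT, either removed at entry or exponential over time.

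The event hazard is λ = ln 2 / 12 = 0.0578 per month.

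**Step 1. Floor, with no accrual assumption.** Remove 30% at entry and give everyone else exactly 24 months:

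76 × 0.70 × (1 − 2⁻²) = 53.2 × 0.75 = 39.9 events.

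Later dropout loses fewer events and earlier entry adds follow-up. So 39.9 is a lower bound for any non-informative dropout of at most 30% in total. It is 14% above 35 (39.9/35 = 1.14).

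**Step 2. Planned accrual, 30% removed at entry.** Follow-up is uniform on 24 to 43 months:

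P(event) = 1 − [e^(−24λ) − e^(−43λ)] / (19λ) = 1 − (0.250 − 0.083)/1.097 = 0.848

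53.2 × 0.848 = 45.1 events.

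**Step 3. Dropout as a competing exponential hazard g.** With k = λ + g:

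expected events = 76 × (λ/k) × {1 − [e^(−24k) − e^(−43k)] / (19k)}

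| Reading of the dropout | Events, 19-month accrual | Events, with 33-month cap |
|---|---|---|
| 30% removed at entry | 45.1 | 44.1 |
| 30% per year, g = −ln(0.7)/12 | 47.2 (32% lost in total) | 46.7 |
| 30% lost overall | 48.3 | 47.6 |
| 30% per 6 months, g = −ln(0.7)/6 | 36.6 (49.5% lost in total) | not computed |

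The first three readings are 29% to 38% above 35 without the cap.

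**Step 4. What gives 35.**
- Removal at entry: without dropout, 76 × 0.848 = 64.5 events. Then 1 − 35/64.5 gives about 46% removed.
- Competing dropout: solving the formula in Step 3 for 35 events gives 54% per year, or about 52% of patients lost in total.

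**Step 5. Precision.** I simulated the Kaplan-Meier median with the SAP's interval, several thousand replicates per scenario, 19-month accrual.

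| Scenario | Chance that width is 11 months or less | Width met with 80% chance (months) |
|---|---|---|
| 53 retained | 0.89–0.90 | 9.8–9.9 |
| 30% per year | 0.91–0.92 | 9.3–9.4 |
| 30% overall | 0.93 | 9.2 |
| 30% per 6 months | 0.77–0.78 | 11.4–11.5 |
| Competing dropout giving 35 events | 0.74 | – |
| 41 retained (about 35 events) | 0.75 | – |
| 40 retained (34 events) | 0.81 | – |

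The 33-month cap leaves the 30% readings at 0.90 to 0.92. The last two rows show that the probability moves unevenly with small changes in the number retained, so near 35 events only the range 0.74 to 0.81 should be relied on.

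**The case against.** The strongest reply is that 9.5 is under-specified rather than wrong, because some readings do come near 35:

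- **30% per 6 months** gives 35.2 events with no accrual period and 36.6 with 19 months. The section does not exclude it, but neither does it state it, and it loses about half the patients. If this was intended, the text still needs correcting.
- **Every dropout is a would-be event, and nobody is followed beyond 24 months.** This gives 76 × (0.75 − 0.30) = 34.2. It is an extreme form of informative dropout, so the 39.9 floor does not cover it. But it also ignores the planned accrual: with that, the same subtraction gives 76 × (0.848 − 0.30) = 41.7, or 40.2 with the 33-month cap.
- **An earlier cut.** Section 12 says "the interim analysis for the primary outcome and some secondary outcomes is planned for Dec 2022". At 12 months after last patient in, with 30% removed at entry, the expected count is 37.1. That is closer, but 9.5 specifies two years.

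The reply is also right that 35 events and about an 80% chance are roughly compatible with each other. Sections 9.5 and 9.9.3 may share a heavier, unstated dropout assumption, so 9.9.3 is not shown to be wrong in isolation. What is shown is that it does not correspond to 30% dropout on the readings tried. Any replacement precision figure depends on the dropout and accrual chosen, which is why both must be stated.

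The limited impact is also conceded. Section 9.9.3 reports enrolment as complete ("76 patients were enrolled in this study, this is a small sample size"), the analysis is descriptive, and no test or trigger depends on 35.

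**Conclusion.** The point holds. With non-informative dropout of at most 30% in total, the inputs in 9.5 give at least 39.9 events. With uniform accrual over the planned 19 months and the three ordinary readings of 30%, they give about 45 to 48, or about 44 to 48 with the 33-month cap. A count of 35 needs about 46% to 52% loss.

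If 30% is right, both figures understate what the study should deliver: the chance of a width of 11 months or less is about 0.89 to 0.93, not 0.80. If 35 is right, dropout is much heavier than stated and the chance is about 0.74 to 0.81, so 80% is at or slightly above what can be expected. The documents do not allow a reader to choose between these.

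Under the stated 30% the error is in the safe direction and N = 76 is not undermined. This is a correction of the sample size justification, not a threat to the primary analysis.

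**What to change.** In Protocol 9.5, state the time scale and pattern of the dropout and the accrual pattern, then restate the expected events: about 45 to 48 if the 30% is removed at entry, per year or overall. If heavier dropout was intended (about 50% overall comes near 35), state that instead.

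In Protocol 9.9.3, derive the precision from the same inputs with the SAP 7.6 interval method. Under the 30% readings this is about a 90% chance of a width of 11 months or less, or equivalently an 80% chance of a width of about 9.2 to 9.9 months.

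The cost is a few sentences of protocol text. N and data collection are unchanged.

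A separate drafting point, which carries no weight in this arithmetic: Protocol 12 plans a December 2022 interim for the primary outcome and SAP 7.6 places the TOT analysis at an interim, while SAP 7.11 says there will be none. One sentence in SAP 7.6 or 7.11, with Protocol 12 aligned, should fix a single data cut for the primary analysis.

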9.6 DATA MANAGEMENT

9.6.1 Electronic data capture system

Data will be gathered in the electronic data capture (EDC) system prepared by the sponsor or appointed CRO. The details of data management procedures to ensure the quality of the data will be described in the statistical and epidemiological analysis plan (SEAP) available in eTMF.

9.6.2 Data entry

All the data will be continuously and directly into the eCRF during or after the patient visit in the whole study period. All reported data from the enrolled investigator's site will be entered via a secured web-based EDC study database. All site personnel will be fully trained in using the EDC system, including eCRF completion guidelines. Site personnel will be provided with secure usernames and passwords in order to enter study data into the EDC system. All participating sites will only have access to view and enter the data for their patients. A data manager will perform concurrent review during the course of the data collection period. Data entered in the eCRFs that are transcribed from source documents must be consistent with the source documents or the discrepancies must be explained. The Investigator may need to request previous medical records or transfer records, depending on the study; also current medical records must be available. For eCRFs all data must be derived from source documents. Data queries generated from the database will be created on an ongoing basis, queries will be based on the data management system logic deck and database validation for adequacy and consistency. The site management team will follow-up to request the completion of such queries.

9.6.3 Statistical software

All analyses will be performed using statistical analysis software (SAS) for Microsoft Windows operating system statistical software (██████████) version 9.3 or higher, using validated implementations of each application or SAS custom programming.

9.7 DATA ANALYSIS

For the purpose of this study, analyses will generally be descriptive in nature and will be conducted using SAS statistical software (version 9.3 or higher). Descriptive data regarding patient demographic and clinical characteristics will be calculated. For categorical measures, data will include the frequency (number of cases (n)) and percentage (%) of total study

patients observed in each category (N). All variables will be summarised descriptively through tabular displays of mean, median, ranges and standard deviations of continuous variables and frequency distributions of categorical variables. When necessary, continuous variables also will be categorised into intervals, with the distribution of patients (n, N, %) for each interval provided.

[figure not shown]
AEs will be graded in accordance with CTCAE Version 5.0. The safety analyses include frequency and intensity of AEs, SAEs and ADRs by System Organ Class (SOC)/Preferred Term (PT) using a current medical dictionary for regulatory activities (MedDRA) dictionary. In addition, AEs resulting in the discontinuation of treatment will be studied.

To assess the presence of channelling bias, we will use the data from study 1200-0066 to assess potential channelling and to put the results into perspective. The baseline characteristics of patients in this study and in study 1200-0066 separately. Patient characteristics will be compared between the two groups using absolute standardised differences (ASD), where an ASD of at least 10% will be considered a meaningful difference.

9.7.1 Main analysis

All patients treated with afatinib will be included in the analysis of the primary outcome, Time on Treatment (TOT) on afatinib. Time on Treatment (TOT) will be evaluated by Kaplan-Meier analysis. Median Time on Treatment (TOT) and two-side 90% CI, and the quartiles will be calculated from the Kaplan-Meier curve. Patients who are lost to follow up without providing the end date of treatment with afatinib will be censored at the time of last known contact.

Overall survival (OS) will be evaluated by Kaplan-Meier analysis. Median overall survival (OS) and two-side 90% CI, and the quartiles will be calculated from the Kaplan-Meier curve. Patients who are lost to follow up (including patient withdrawal) without providing the end date of treatment will be censored at the time of last known contact. Patients who reach the end of study period without providing the end date of treatment will be censored at the end of study.

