9.9.1 Lost to follow-up

All patients will be followed up until the event of OS. If a patient misses more than 1 clinic care visit, the site will attempt to communicate with the patient and document the patient's reason for not returning. Sites will be requested to contact patients at various times of the day and evening and on different days of the week. If the patient cannot be contacted after the due diligence process, the treating physician will attempt to contact the patient's designated secondary contacts, including the patient's general practitioner and next-of-kin or out-of-household contacts to obtain information on the patient's whereabouts and vital status. If the patient's care has been transferred to another healthcare professional, the treating physician at the enrolling site will be responsible for obtaining the required follow-up information from the new treating physician. Patients who do not return for at least 2 scheduled visits, and for whom no information is available will be considered lost to follow-up and will be censored at time of last visit or last known contact with the healthcare provider.. Follow-up information collecting could be accepted by phone call if the information is available and complete.

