7.7 SECONDARY ANALYSES

7.7.1 OS from the start of afatinib until the date of death

OS is defined as the time from the start of afatinib until death for any reason. Subjects who have not died at the time of the statistical analysis will be censored at the time they were last known contact.

OS will be analyzed in a similar fashion with primary analysis. Analysis will be provided for population set TS.

The swimlane plot of overall survival by subsequent treatment will be provided.

For the purposes of displaying the subsequent treatment duration in plot, incomplete second line treatment start/end and third line treatment start dates will be imputed as below:

If month and year are present and day is missing for treatment start date:

Proprietary confidential information © 2024 Boehringer Ingelheim International GmbH or one or more of its affiliated companies

- Set day to the first day of month

If month and year are present and day is missing for treatment end date:

- If year=year of treatment start date and
 - If month = month of treatment start date then set day to last day of month
 - If month > month of first dose then set day to first day of month

For all other cases, the missing dates will not be imputed and partial dates will not be displayed on plot.

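### The SAP's last-contact derivation can keep lost or withdrawn patients at risk for OS after they were last known alive, and the protocol's OS censoring rule carries a condition that belongs to time on treatment

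*Protocol*

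**What the plan says.** **SAP 7.7.1 (OS).** "Subjects who have not died at the time of the statistical analysis will be censored at the time they were last known contact". The section adds that "OS will be analyzed in a similar fashion with primary analysis". It does not derive the contact date. SAP 6.6 points to 7.7.1 for incomplete OS dates, but the only imputation there is for subsequent-treatment dates in the swimlane plot.

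**SAP 7.6 (TOT).** This is the only place where last known contact is derived. For patients who withdrew or were lost, it is the last assessment or visit date "or the date of the last dose of study drug or end of study date, whichever occurs later", capped at the cut-off date.

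**Protocol 9.9.1.** "Patients who do not return for at least 2 scheduled visits", and about whom nothing is known, count as lost and "will be censored at time of last visit or last known contact with the healthcare provider".

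**Protocol 9.7.1 (OS paragraph).** Lost or withdrawn patients with no treatment end date are censored at last known contact. For the rest: "Patients who reach the end of study period without providing the end date of treatment will be censored at the end of study".

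**SAP section 4** declares no change to the planned analysis.

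**The concern.** There are two separate faults.

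The first is in the SAP. Taking the latest of three dates is harmless only if each of them is a date on which the patient was known to be alive. A visit or a dose meets that test. An end-of-study date meets it only if someone confirmed vital status that day. Otherwise the patient stays in the risk set over an interval in which a death would not be seen. That inflates the Kaplan-Meier denominators without adding events, so the curve and its median can move only upward.

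The second is in the protocol. Having no treatment end date is a sensible condition for censoring TOT, but it says nothing about vital status. Read literally, the OS paragraph has no rule for a patient who has stopped afatinib and is alive. It also uses the end of study for patients who get that far, where SAP 7.7.1 uses last known contact, and SAP section 4 does not record the difference.

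At stake is the OS curve, a named secondary outcome, including how often its median is reported as not reached.

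**Working it through.** The documents give no planned OS median, event count or OS loss rate, so there is no OS figure to reproduce. The OS inputs below are assumptions.

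**1. How far the date can run past contact.** Loss is declared after at least 2 missed scheduled visits (protocol 9.9.1). SAP 6.7 gives a 28-day visit window on first-line treatment. An exit date entered when loss is declared would then fall about 2 × 28 = 56 days, or roughly 2 months, after the last contact. Later lines follow institutional schedules, so the lag could be longer. I used 2 to 6 months. The cut-off cap does not help, because the unobserved interval lies before the cut-off.

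**2. Effect on median OS at the study's size.** Simulated studies of 76 patients (protocol 9.5). Accrual is uniform over 19 months (May 2020 to December 2021) and data end at month 43 (December 2023), both from protocol section 6. Assumed: exponential OS with median 30 months; 10%, 20% or 30% of patients given a loss time at random over their possible follow-up; deaths after loss unseen. Replicates with the median not reached are kept as infinite. Dropping them would pull the baseline down to about 29.4; with them kept, censoring at the last real contact gives about 30.

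| Patients lost | Rise in median, date 2-6 months after contact | Rise in median, date = calendar study end |
|---|---|---|
| 10% | 0.1-0.4 months | 1.7 months |
| 20% | 0.4-1.3 months | 4.7 months |
| 30% | 0.5-1.9 months | 7.4 months |

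Under the calendar reading, the share of studies with median not reached goes from 8-10% to 13-37%. Repeat runs agree to within about 0.4 months.

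**3. Large-sample check with other medians.** 400,000 patients per setting, exponential loss of 10%, 20% or 30% by month 24. Besides 24 months, I used 31.4 and 33.3 months, the Del19 subgroup medians quoted in the protocol abstract, for illustration only.

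| Assumed median | Last real contact | 2 months later | Calendar study end |
|---|---|---|---|
| 24 | 24.0 / 24.0 / 24.0 | 24.2 / 24.4 / 24.7 | 25.8 / 28.3 / 32.5 |
| 31.4 | 31.4 / 31.3 / 31.5 | 31.7 / 31.9 / 32.5 | 34.6 / 39.4 / not reached |
| 33.3 | 33.3 / 33.2 / 33.4 | 33.6 / 33.9 / 34.4 | 36.9 / 42.9 / not reached |

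Censoring at last real contact recovers the assumed median. A 2-month lag adds 0.2 (24.2 − 24.0) to 1.0 months (34.4 − 33.4).

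**4. Who falls outside the protocol's literal OS rule.** With the plan's exponential TOT, median 12 months (protocol 9.5), and follow-up uniform over 24-43 months, the share still on afatinib at study end is (0.5^(24/12) − 0.5^(43/12)) / (19 × ln 2 / 12) = (0.250 − 0.083) / 1.097 ≈ 0.152, or 76 × 0.152 ≈ 11.5 patients. The same formula with an assumed OS median of 24 months gives about 29.2 alive; with 33.3 months, about 38.1. Survivors off afatinib are then 1 − 11.5/29.2 ≈ 61% to 1 − 11.5/38.1 ≈ 70%. So, with no loss to follow-up, 60-70% of survivors would have a treatment end date and meet neither OS censoring sentence in 9.7.1.

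**The case against.** **A reader might infer that the protocol sentence on patients who reach study end itself overstates OS.** It does not. Censoring such patients there is ordinary administrative censoring if vital status is confirmed, and the flow chart schedules vital status in the end-of-study column. For lost or withdrawn patients the same paragraph uses last known contact. Nor is the treatment end date ever the censoring date; it appears only as a condition. The route to overstatement is SAP 7.6.

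**A reader might also infer that OS is certain to be overstated, or by several months.** The documents do not support that. Neither defines *end of study date*. It is listed beside the patient's own last visit and last dose, and protocol 11.2 speaks of an individual patient's end of study. If the calendar end were meant, the later-of rule would almost always select it and the other two dates would be redundant. A patient-level exit date is the more natural reading, and for a withdrawal it may be the day of contact itself, with no lag at all.

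**The derivation sits under TOT.** True, but 7.7.1 uses the same term, defines no other, and refers back to the primary analysis.

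**The protocol gap is closed elsewhere.** Largely so: the OS definitions, 9.9.1 and SAP 7.7.1 carry no treatment-end condition. The rule in 9.7.1 still needs correcting, because it conflicts with them.

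**The effect is small against the noise.** In the same simulation the 90% CI for median OS is about 14 months wide when finite, and its upper limit is not reached in over half of runs. OS is secondary in a descriptive study with no group comparison. Also, the 30% drop-out in protocol 9.5 was stated for sizing TOT, not as an OS loss rate. These points limit the importance, but the shift is a bias in one direction and is cheap to remove.

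**Conclusion.** The point stands in a conditional form. As written, SAP 7.6 lets a lost or withdrawn patient be counted at risk for OS after the last date known alive, against protocol 9.9.1, so OS **can** be overstated. On the natural reading of a patient-level exit date 2-6 months after contact, the median rises by about 0.1-0.4 months with 10% lost, 0.4-1.3 with 20% and 0.5-1.9 with 30%. The larger shifts need the calendar-end reading, which the documents do not rule out but which fits their wording less well. If every end-of-study date coincides with a contact, there is no bias.

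These sizes rest on an exponential OS with median 30 months, loss unrelated to prognosis, and loss rates of 10-30%, none of which the documents supply for OS.

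The treatment-end condition in protocol 9.7.1 is a drafting error whatever the size. So is the unrecorded difference from SAP 7.7.1 for patients who reach study end. The changes should be made before OS is analysed, but nothing here affects the definition of the primary outcome.

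**What to change.** 1. In protocol 9.7.1 and SAP 7.7.1, state one OS rule: patients not known to have died are censored at the date last known alive, meaning the latest documented visit, assessment, dose or other contact confirming vital status, and not later than the cut-off.
2. Delete the treatment-end condition from the protocol's OS paragraph.
3. Give OS its own date derivation in SAP 7.7.1. Let an end-of-study date count only if vital status was confirmed on that date, and say whether the term means the patient's exit or the study's end.
4. Record the alignment in SAP section 4.

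The 7.6 derivation also sets TOT censoring. A separate OS derivation leaves TOT untouched; if 7.6 itself is edited, check the effect on TOT first.

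The cost is a few sentences and a small programming change. Visits, doses and vital status are already planned for collection; whether the eCRF dates each vital-status confirmation should be checked. Reported OS may be slightly shorter.
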